9.2. REPORTING OF ADVERSE EVENTS (AEs)

Report initiation for all AEs and SAEs will begin at the time of the first treatment visit and continue until the end of final study visit. All events will be followed to resolution or until the subject completes the study. A final assessment of outcome will be made at that time.

All AEs must be recorded in the subject's medical records and on the CRF. AEs will be reported using customary medical terminology along with the following information: the onset and end dates, whether the event is considered to be a SAE (see [Section 9.3](#)), the impact the event had on study treatment (see [Section 9.2.1](#)), the Common Terminology Criteria for Adverse Events (CTCAE) grade (intensity) of the event (see [Section 9.2.2](#)), the causality of the event (see [Section 9.2.3](#)), whether treatment was given as a result of the event (see [Section 9.2.4](#)), and the outcome of the event (see [Section 9.2.5](#)).

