4.2. SCREENING PHASE

The subject (or Legally Acceptable Representative (LAR)) will sign and date the informed consent form (ICF) and Health Insurance Portability Accountability Act (HIPAA) authorization (according to site policy and practices) prior to any study-related procedures. All study centers will be instructed to maintain the study-specific screening and enrollment logs at their sites.

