4.2.1. Screening Visit: Up to 28 days

Subjects will be screened for enrollment within 28 days prior to Treatment Cycle 1, Day 1.

The assessments described in this section will be the same for both Part 1 and Part 2 of the study, unless otherwise noted.

Subjects will be screened in accordance with predefined entrance criteria as described in [Section 3.4](#). The following procedures will be performed at Screening:

- [REDACTED]
- [REDACTED]
- [REDACTED]
- [REDACTED]
- [REDACTED]
- [REDACTED]
- [REDACTED]
- [REDACTED]
- [REDACTED]
- [REDACTED]
- [REDACTED]
- [REDACTED]
 - [REDACTED]
 - [REDACTED]
 - [REDACTED]
[REDACTED]
- [REDACTED]
 - [REDACTED]
 - [REDACTED]
 - [REDACTED]

■ [REDACTED]

All subjects who fail to meet eligibility criteria are considered screen failures and are exited from the study without further evaluation.

Note: If a subject initially fails to meet inclusion/exclusion criteria and is later reconsidered for participation, the subject will be re-consented and assigned a new unique identification number at the time of re-screening. Subjects who fail their first screening attempt may be re-screened a maximum of once and may be enrolled if they are found to meet all inclusion and no exclusion criteria when re-screened.

All screening information for subjects who meet eligibility criteria will be transcribed onto the appropriate page of the Case Report Form (CRF). See [Section 7.2.1](#) for procedures for documenting screening failures.

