7.2.1. Re-screening

A subject who signed a consent form but did not meet the inclusion/exclusion criteria is classified as a screen failure.

Note: If a subject initially fails to meet inclusion/exclusion criteria and is later reconsidered for participation, the subject will be re-consented and assigned a new unique identification number at the time of re-screening. Subjects who fail their first screening attempt may be re-screened a maximum of once and may be enrolled if they are found to meet all inclusion and no exclusion criteria when re-screened.

For consented subjects who do not meet eligibility criteria, a Screen Failure Case Report Form (CRF) will be completed. The Screen Failure CRF will contain the following details: the subject identification number, the date of ICF signature, demographic information (see [Section 7.3](#)), and the reason for screen failure. No additional information will be required for subjects who fail screening.

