7.4. MEDICAL HISTORY

A medical history will be recorded during the Screening Phase and will include:

- All ongoing medical conditions
- All previously resolved medical conditions that are relevant in the judgment of the Investigator
- Any prior medical conditions that have resolved within the last year

Events that emerge prior to the first treatment will be recorded in the medical history and not as AEs. Aside from being used to determine subject eligibility, this information will permit the Investigator to record the nature, duration, and severity of any ongoing baseline medical conditions prior to the subject's receiving investigational product treatment.

For each relevant history, the following will be documented:

- Disease/disorder/condition
- Date of diagnosis
- History status (resolved or ongoing).

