9.1. ADVERSE EVENT (AE) DEFINITION

An adverse event (AE) is defined as any unfavorable or unintended sign, symptom, or disease that occurs or is reported by the patient to have occurred, or a worsening of a pre-existing condition. An adverse event may or may not be related to the study treatment.

AEs will be elicited through direct questioning and subject reports. Any abnormality in physical examination findings or laboratory results that the investigator believes is clinically significant (CS) to the research subject and that occurred after initiation of the first study treatment will be reported as AEs. Abnormal findings that are NOT clinically significant should not be recorded as an AE.

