9.2.3. Event Causality Assessment

AEs will be assigned a relationship (causality) to the study treatment. The Investigator will be responsible for determining the relationship between an AE and the study treatment. The type of event, organ system affected, and timing of onset of the event will be factors in assessing the likelihood that an AE is related to the study treatment. Relationship of AEs to study treatment will be classified as follows:

- 1. Definitely related:** This category applies to those AEs that the Investigator feels are incontrovertibly related to the study treatment. An AE may be assigned an attribution of definitely related if or when it meets all of the following criteria: (1) it follows a reasonable temporal sequence from administration of the study treatment; (2) it could not be reasonably explained by the known characteristics of the subject's clinical state, environmental or toxic factors, or other modes of therapy administered to the subject; (3) it follows a known response pattern to treatment with the study treatment.
- 2. Probably related:** This category applies to those AEs which, after careful medical consideration at the time they are evaluated, are felt with a high degree of certainty to be related to the study treatment. An AE may be considered probable if or when (must have three): (1) it follows a reasonable temporal sequence from administration of the study treatment. (2) It could not readily have been produced by subject's clinical state, environmental or toxic factors, or other therapies administered to the subject. (3) Disappears or is decreased upon discontinuation of the study treatment. (4) It follows a known response pattern to treatment with the study treatment.
- 3. Possibly related:** This category applies to those AEs which, after careful medical consideration at the time they are evaluated, are judged unlikely but cannot be ruled out with certainty to the study treatment. An AE may be considered possible if or when (must have two): (1) it follows a reasonable temporal sequence from administration of the study treatment. (2) It could not

readily have been produced by subject's clinical state, environmental or toxic factors, or other therapies administered to the subject. (3) Disappears or is decreased upon discontinuation of the study treatment. (4) It follows a known response pattern to treatment with the study treatment.

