9.4. REPORTING OF SERIOUS ADVERSE EVENTS (SAEs)

The Investigator is required to report all SAEs that occur during the time period specified in [Section 9.2](#). Once the Investigator becomes aware of an SAE, he/she must report the SAE to Medical Monitor within 24 hours.

Attn: Amarex Clinical Research, LLC
[name]
[name]

The Medical Monitor may request additional supporting documentation as it becomes available, such as lab reports, electrocardiogram [ECG] reports, discharge summary, hospital notes, etc., if applicable. Additional follow-up information as it becomes available must be reported to the Medical Monitor.

The Investigator is also responsible for reporting all SAEs to the appropriate Institutional Review Board (IRB) in accordance with local laws and regulations. The Investigator is responsible for maintaining documentation in the study file that indicates the IRB has been properly notified.

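### A serious event caused by a study procedure between consent and the first treatment visit has no AE or SAE form and no 24-hour report to the medical monitor

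*Protocol*

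**What the plan says.** The rule is spread over several protocol sections, and all of it is readable.

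- **Consent (4.2)** is signed "prior to any study-related procedures".
- **Screening (4.2.1):** "Subjects will be screened for enrollment within 28 days prior to Treatment Cycle 1, Day 1".
- **Medical history (7.4):** "Events that emerge prior to the first treatment will be recorded in the medical history and not as AEs".
- **AE definition (9.1):** examination and laboratory abnormalities judged clinically significant count only if they are ones "that occurred after initiation of the first study treatment will be reported as AEs".
- **Reporting window (9.2):** "Report initiation for all AEs and SAEs will begin at the time of the first treatment visit". It runs to the final study visit.
- **SAE definition (9.3):** an SAE is an AE that meets one of the listed seriousness criteria.
- **SAE reporting (9.4):** "The Investigator is required to report all SAEs that occur during the time period specified in" Section 9.2. Within that period the medical monitor must be told within 24 hours. A separate sentence covers IRB reporting.
- **Causality (9.2.3):** "AEs will be assigned a relationship (causality) to the study treatment". Study procedures have no category.
- **Screen failures (7.2.1):** the CRF holds the subject number, consent date, demographics and reason for failure. "No additional information will be required for subjects who fail screening". Section 11.2 confirms that only the screen-failure page is completed.

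SAP Section 8.3.1 counts TEAEs from first treatment, and its readable text adds no category for events before dosing.

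**The concern.** Starting general AE collection at first dose is a legitimate choice. The difficulty is that the plan makes no exception for harm done by the study itself before dosing. From consent onward a person undergoes procedures because the protocol requires them. If one of these causes serious injury, the medical monitor should hear of it, because the same procedure is about to be performed on the next subject. The plan provides no such report.

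Participant protection is at stake here, not the estimation of any endpoint. The protocol has no independent data monitoring committee (Section 12 marks it not applicable), so the route to the medical monitor carries more weight than it might elsewhere.

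**Working it through.** The plan states no figure to reproduce and no arithmetic applies. The check is to follow one hypothetical event, a serious injury from a screening procedure, through each rule.

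1. **Is it in the period the plan covers?** Consent comes first (4.2), and screening may take up to 28 days before Cycle 1 Day 1 (4.2.1). Reporting starts at the first treatment visit (9.2). The event falls before that start.
2. **Is it an AE?** The general definition in 9.1 has no time limit, but 7.4 is explicit that an event before first treatment is not recorded as one, and 9.2 does not open the window until later.
3. **Is it an SAE?** Under 9.3 an SAE is a kind of AE. An event that 7.4 says is not to be recorded as an AE does not become an SAE by being serious.
4. **Does the 24-hour duty apply?** Section 9.4 limits it to the period in 9.2, so it does not.
5. **What is recorded if the subject goes on to treatment?** Medical history (7.4) documents the condition, date of diagnosis and whether it is resolved or ongoing, and is meant to let the investigator note the nature, duration and severity of ongoing conditions. An AE record under 9.2 would also carry seriousness, CTCAE grade, causality, treatment given and outcome.
6. **What is recorded if the subject fails screening?** Only the items in 7.2.1. Section 4.2.1 transcribes screening information only for subjects who meet eligibility, and 11.2 limits failures to one CRF page. The reason for failure may hint at the event; no other item would.
7. **Could relationship to a procedure be recorded at all?** Section 9.2.3 relates events to study treatment only.
8. **Do the start points agree?** Section 7.4 uses first treatment and 9.2 uses the first treatment visit. An event on Cycle 1 Day 1 before dosing falls under both: inside the reporting window by 9.2, medical history by 7.4.

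**Who is exposed:** up to 16 + 24 = 40 treated subjects, for up to 28 days each, plus every consented subject who fails screening, whose number the documents do not give. One re-screen is allowed under a new identification number (7.2.1), so some people may pass through the gap twice.

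**The case against.** The case against is that this is a consistent design choice: Sections 7.4, 9.1, 9.2 and 9.4 and the SAP all count from about the same point, and no statistical result depends on it. That is true, and it limits how much weight the point should carry. It does not supply a reporting route.

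Several stronger readings are tempting, and the documents do not support them.

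- **A reader might infer that the event would go unrecorded everywhere.** Section 14.1 makes the subject's medical record the primary source document, so the site may well hold it, and the screen-failure reason may show a trace.
- **A reader might infer that the IRB would not be told.** The 24-hour duty in 9.4 runs to the medical monitor. The IRB sentence is separate, refers to local laws and regulations, and does not repeat the 9.2 window. Because 9.3 makes every SAE an AE, one can argue that the protocol creates no IRB duty here, but local law may, and the point is not settled by the text.
- **A reader might infer that screening carries substantial risk.** The procedure list in 4.2.1 and the row labels of the assessment schedules are redacted. Inclusion criterion 3 asks for an available tumor biopsy, which does not establish that a new one is taken.
- **A reader might infer that a screening event continuing into Cycle 1 is lost to the safety data.** Section 9.1 counts worsening of a pre-existing condition as an AE, so a deterioration after dosing is captured. An event that persists unchanged stays as baseline history.

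**Conclusion.** The gap is real and narrow. For up to 28 days per screening attempt, a serious event caused by a protocol-required procedure has no AE or SAE form and no 24-hour report to the medical monitor. In a screen failure it appears on no study CRF except possibly as the reason for failure.

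This rests on readable text alone and assumes that no redacted passage makes an exception. How often it would matter cannot be judged without the list of screening procedures, and the documents give no event rate or screen-failure rate from which to estimate it. The MTD, DLT and TEAE analyses all count from treatment and are unaffected. The change is worth making because it protects consented people at little cost; the primary endpoint is not in question.

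**What to change.** 1. **Sections 9.2 and 9.4:** from signature of the consent form to first dose, record any SAE that the investigator relates to a protocol-required procedure, including a fatal one, and report it to the medical monitor within 24 hours. Leave general AE and SAE collection from first treatment as it is.
2. **Section 7.4:** exempt these events from the medical-history rule.
3. **Section 9.2.3:** add relationship to study procedure. Without it, the investigator has no way to record the judgment on which item 1 depends.
4. **Sections 7.2.1 and 11.2:** add an SAE field to the Screen Failure CRF.
5. **Sections 7.4 and 9.2:** use one start point, so that an event before dosing on Cycle 1 Day 1 falls under one rule only.
6. **Reporting:** show these events in a separate by-subject listing. The SAP's TEAE definition stays unchanged.

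The cost is a protocol amendment of a few sentences, the matching CRF fields, one listing and probably a small number of extra reports.

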9.2.1. Impact on Study Treatment

The impact the event had on the study treatment will be assessed as either: dose increased, dose not changed, dose rate reduced, dose reduced, drug interrupted, drug withdrawn, not applicable, or unknown. The "not applicable" assessment will be used only when the subject is no longer in the Treatment Phase of the protocol.

9.2.2. CTCAE Grade (Intensity) Assessment

The guidelines outlined in CTCAE v5.0 will be used for assessing the intensity of the event. The general guidelines for assessing the AE grade appear below. Full guidelines may be obtained at <http://evs.nci.nih.gov/ftp1/CTCAE>.

Table 9-1: CTCAE v5.0 General Guidelines

Grade	Description
Grade 1	Mild; asymptomatic or mild symptoms; clinical or diagnostic observations only; intervention not indicated.
Grade 2	Moderate; minimal, local or noninvasive intervention indicated; limiting age-appropriate instrumental activities of daily living (ADL)*.
Grade 3	Severe or medically significant but not immediately life-threatening; hospitalization or prolongation of hospitalization indicated; disabling; limiting self-care ADL†.
Grade 4	Life-threatening consequences; urgent intervention indicated.
Grade 5	Death related to AE.

*Instrumental ADL refer to preparing meals, shopping for groceries or clothes, using the telephone, managing money, etc.

†Self-care ADL refer to bathing, dressing and undressing, feeding self, using the toilet, taking medications, and not bedridden.

-Common Terminology Criteria for Adverse Events (CTCAE), v5.0: November 27, 2017

9.2.3. Event Causality Assessment

AEs will be assigned a relationship (causality) to the study treatment. The Investigator will be responsible for determining the relationship between an AE and the study treatment. The type of event, organ system affected, and timing of onset of the event will be factors in assessing the likelihood that an AE is related to the study treatment. Relationship of AEs to study treatment will be classified as follows:

- 1. Definitely related:** This category applies to those AEs that the Investigator feels are incontrovertibly related to the study treatment. An AE may be assigned an attribution of definitely related if or when it meets all of the following criteria: (1) it follows a reasonable temporal sequence from administration of the study treatment; (2) it could not be reasonably explained by the known characteristics of the subject's clinical state, environmental or toxic factors, or other modes of therapy administered to the subject; (3) it follows a known response pattern to treatment with the study treatment.
- 2. Probably related:** This category applies to those AEs which, after careful medical consideration at the time they are evaluated, are felt with a high degree of certainty to be related to the study treatment. An AE may be considered probable if or when (must have three): (1) it follows a reasonable temporal sequence from administration of the study treatment. (2) It could not readily have been produced by subject's clinical state, environmental or toxic factors, or other therapies administered to the subject. (3) Disappears or is decreased upon discontinuation of the study treatment. (4) It follows a known response pattern to treatment with the study treatment.
- 3. Possibly related:** This category applies to those AEs which, after careful medical consideration at the time they are evaluated, are judged unlikely but cannot be ruled out with certainty to the study treatment. An AE may be considered possible if or when (must have two): (1) it follows a reasonable temporal sequence from administration of the study treatment. (2) It could not

readily have been produced by subject's clinical state, environmental or toxic factors, or other therapies administered to the subject. (3) Disappears or is decreased upon discontinuation of the study treatment. (4) It follows a known response pattern to treatment with the study treatment.

- 4. Unlikely related:** In general, this category can be considered applicable to those AEs which, after careful medical consideration at the time they are evaluated, are judged likely to be unrelated to the study treatment. An AE may be considered unlikely if or when (must have two): (1) it does not follow a reasonable temporal sequence from administration of the study treatment. (2) It could not readily have been produced by subject's clinical state, environmental or toxic factors, or other therapies administered to the subject. (3) Disappears or is decreased upon discontinuation of the study treatment. (4) It does not follow a known response pattern to treatment with the study treatment.
- 5. Unrelated:** This category applies to those AEs which, after careful consideration at the time they are evaluated, are clearly and incontrovertibly due to extraneous causes (disease, environment, etc.) and determined with certainty to have no relationship to the study treatment.

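### Two of the four criteria for 'Unlikely related' are evidence for relatedness, so the checklist contradicts its own category

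*Protocol*

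**What the plan says.** Protocol 9.2.3 makes the investigator responsible for causality and defines five categories. 'Definitely related' needs three features together: plausible timing, no other reasonable explanation and a known response pattern. The next three categories each give four numbered criteria and a minimum count.

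- 'Probably related' needs three: "An AE may be considered probable if or when (must have three): (1) it follows a reasonable temporal sequence". Its last two criteria read "3) Disappears or is decreased upon discontinuation of the study treatment. (4) It follows a known response pattern to treatment".
- 'Possibly related' needs two: "An AE may be considered possible if or when (must have two): (1) it follows a reasonable temporal sequence". Criteria (2) to (4) are worded as in 'Probably related'.
- 'Unlikely related' needs two: "An AE may be considered unlikely if or when (must have two): (1) it does not follow a reasonable temporal sequence". Its second criterion is "2) It could not readily have been produced by subject's clinical state, environmental or toxic factors, or other therapies administered to the subject", and the last two are "3) Disappears or is decreased upon discontinuation of the study treatment. (4) It does not follow a known response pattern to treatment".

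'Unrelated' has no checklist; it requires certainty that the cause lies elsewhere. The text introducing 'Unlikely related' reserves it for events that the investigator considers probably not due to treatment. Protocol 9.2 requires a causality assessment for every adverse event.

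**The concern.** Between 'Possibly' and 'Unlikely', criteria (1) and (4) change direction, as they should. Criteria (2) and (3) do not: they are the same statements that support relatedness in the two categories above. An event with no other explanation that improves when treatment stops therefore meets the count for 'Unlikely' whatever its timing and pattern. In the other direction, an event with plausible timing, an evident other cause, no improvement off drug and no known pattern meets only one 'Unlikely' criterion.

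The checklists are the only operational guidance visible in the protocol for separating these categories. Safety and tolerability are secondary objectives (Protocol 2.1.2), and the trial has no randomization (8.4) and no data monitoring committee (section 12). Attribution therefore rests on individual assessment without a concurrent control. If the written rule lets the same facts support opposite codes, the causality field cannot be read consistently across investigators at up to five centers, and a monitor has no textual basis for a query.

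**Working it through.** The plan gives no figure to reproduce, so the check is an enumeration of the rules in Protocol 9.2.3.

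**Inputs.** Four yes/no features (1 = yes):
- T: reasonable timing
- E: no other explanation
- D: disappears or decreases off drug
- K: known response pattern

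**Rules as written**, with r = T + E + D + K and the required counts read as minimums:
- Definite: T = E = K = 1
- Probable: r ≥ 3
- Possible: r ≥ 2
- Unlikely: u = (1 − T) + E + D + (1 − K) ≥ 2

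**Corrected Unlikely**, with (2) and (3) negated: u* = (1 − T) + (1 − E) + (1 − D) + (1 − K) = 4 − r ≥ 2.

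| T E D K | r | Categories 1–3 met | u | Unlikely as written | u* | Unlikely corrected |
|---|---|---|---|---|---|---|
| 1 1 1 1 | 4 | Definite, Probable, Possible | 2 | yes | 0 | no |
| 1 1 1 0 | 3 | Probable, Possible | 3 | yes | 1 | no |
| 1 1 0 1 | 3 | Definite, Probable, Possible | 1 | no | 1 | no |
| 1 0 1 1 | 3 | Probable, Possible | 1 | no | 1 | no |
| 0 1 1 1 | 3 | Probable, Possible | 3 | yes | 1 | no |
| 1 1 0 0 | 2 | Possible | 2 | yes | 2 | yes |
| 1 0 1 0 | 2 | Possible | 2 | yes | 2 | yes |
| 1 0 0 1 | 2 | Possible | 0 | no | 2 | yes |
| 0 1 1 0 | 2 | Possible | 4 | yes | 2 | yes |
| 0 1 0 1 | 2 | Possible | 2 | yes | 2 | yes |
| 0 0 1 1 | 2 | Possible | 2 | yes | 2 | yes |
| 1 0 0 0 | 1 | none | 1 | no | 3 | yes |
| 0 1 0 0 | 1 | none | 3 | yes | 3 | yes |
| 0 0 1 0 | 1 | none | 3 | yes | 3 | yes |
| 0 0 0 1 | 1 | none | 1 | no | 3 | yes |
| 0 0 0 0 | 0 | none | 2 | yes | 4 | yes |

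**Counts from the table:**

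| | As written | (2) and (3) negated |
|---|---|---|
| Definite also Unlikely | 1 of 2 | 0 of 2 |
| Probable also Unlikely | 3 of 5 | 0 of 5 |
| Possible also Unlikely | 8 of 11 | 6 of 11 |
| E = D = 1 and Unlikely | 4 of 4 | 1 of 4 |
| None of categories 1–4 | 2 | 0 |

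As written, an event with all four relatedness features meets all four checklists at once. The two patterns without a home are 1000 and 0001.

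The residual 6 follows from the thresholds: with u* = 4 − r, both Possible and Unlikely hold exactly when r = 2, and 4 × 3 / 2 = 6 patterns have two features. If the highest category met is then assigned, the 16 patterns separate cleanly: Definite 2, Probable 5 − 2 = 3, Possible 11 − 5 = 6, Unlikely 16 − 11 = 5, and 2 + 3 + 6 + 5 = 16. A precedence rule alone, without the negation, would leave the 2 patterns unplaced and the contradictory text in force.

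**The case against.** The strongest reply is that the checklist does not decide the code. The language is permissive, category 4 opens with a general description, and the investigator must first think the event is probably not due to treatment. On that reading the count of two is a necessary condition, and no sensible investigator would use 'Unlikely' for an event with all four relatedness features. This largely stands: the rule allows a wrong code and does not compel one. It does not cure the defect, because the prose does not separate the categories either. The description of 'Possibly related' itself speaks of events thought unlikely to be due to treatment but not excludable, so the Possible/Unlikely boundary falls back on the lists.

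Two stronger readings are tempting.

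- **DLT counts.** A reader might infer that the error reaches dose escalation, since at six subjects one DLT allows escalation and two stop it (Protocol 3.1). The DLT definition is redacted, so the documents do not show whether relatedness enters it. SAP 8.2.1.2 mentions only toxicity grading, and SAP 8.2.1.1 has the sponsor determine the MTD in consultation with a safety assessment committee.
- **Favourable bias.** A reader might infer that drug toxicity will be under-attributed. The overlap permits that, but the two patterns without a home could be coded upwards instead, or as 'Unrelated' if the cause is certain. The net direction is unknown.

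The visible safety outputs also do not depend on causality: TEAEs are defined by onset date and all adverse events are listed (SAP 8.3.1). Any related-event summaries are redacted, so no specific table can be shown to be affected.

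**Conclusion.** Wrong as written. Criteria (2) and (3) of category 4 contradict the category's own description, and no visible text in either document corrects them. The size is the pattern overlap shown above. Patterns are weighted equally and say nothing about how often each occurs, so the counts are not error rates.

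The conclusion assumes that each feature can be answered yes or no, that the required counts are minimums, and that the no-other-explanation requirement in 'Definitely related', which is worded slightly differently, is the same feature as criterion (2). The contradiction itself needs none of these assumptions, since it is visible when the lists are set side by side. What is established is that recorded causality is unreliable in either direction. An effect on DLT counts, the MTD or any related-event table is not established.

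**What to change.** Amend category 4 of Protocol 9.2.3:

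1. Reverse criterion (2), so that it is met when the patient's condition, environmental or toxic exposures, or another therapy could readily account for the event.
2. Reverse criterion (3), so that it is met when the event neither resolves nor lessens after study treatment is stopped.
3. Add a precedence rule, for example that the highest relatedness category whose criteria are met is assigned. The two reversals alone do not separate 'Possible' from 'Unlikely', because both need only two of four criteria.

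Align any site guidance that repeats the list. The cost is a short amendment and a site note, plus re-review of causality for events already coded 'Unlikely', best done before database lock.
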